#### **10.2.7.2. Treatment of Bleeding Episodes During Immune Tolerance Induction Therapy**

At the Investigator's discretion, activated prothrombin complex concentrates, recombinant activated coagulation factor VII, and rFVIII Fc can be used to treat active bleeding or to provide surgical hemostasis during ITI.

#### **10.2.7.3. Interruption of Immune Tolerance Induction Therapy**

Interruptions of ITI should be avoided wherever possible and not exceed a maximum of 2 weeks. Subjects who discontinue ITI after less than 33 months will be withdrawn from study, unless they have already met the criteria for successful immune tolerance described in Section 10.2.7.4 .

#### **10.2.7.4. Immune Tolerance Induction Therapy Outcomes**

The outcome of ITI (complete success, partial success, or failure) will be assessed in the study via the algorithm provided in Figure 2. Potential outcomes are defined below.

##### **10.2.7.4.1. Reference Incremental Recovery Values for ITI**

The reference IR Value (expected recovery), which is the basis for one of the criteria for complete ITI success, is defined below:

- For subjects who have a baseline IR value,  $\geq 66\%$  of the subject's baseline value (if the subject's baseline IR value was obtained via the Baseline IR visit), OR

- 

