##### **10.2.7.4.2. Definitions of Complete Success, Partial Success, and Failure of Immune Tolerance Induction Therapy**

###### **Complete Success:**

CONFIDENTIAL

The information contained herein may not be used, disclosed, or published without the written consent of Bioerativ Therapeutics Inc.

Complete ITI success requires that all of the following criteria be met:

1. Negative inhibitor titers in 2 consecutive determinations at least 1 month apart
13. IR  $\geq$ 66% of expected in 2 consecutive determinations at least 1 month apart
14.  $t_{1/2} \geq$ 6 hours

Subjects may meet the criteria for complete success in less than 33 months.

Subjects fulfilling the criteria for complete success will transition to a “tapering” regimen over a minimum period of 12 weeks with the aim of starting a prophylactic rFVIII Fc regimen, as described in Section 10.2.7.5, and will be monitored for relapse for up to 9 months as described in Section 4.2.2.5.

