**Partial Success:**

The determination of partial success will be made only for subjects who have completed 33 months of ITI but who do not fulfill the criteria for complete success.

To achieve partial success, the following criteria must be met after subjects have completed 33 months of ITI:

1. Negative inhibitor titers on 2 consecutive tests within 2 months of each other

AND

15. Either of the following but not both:

- IR  $\geq$ 66% of expected

OR

- $t_{1/2} \geq$ 6 hours

If the subject has 2 negative inhibitor tests but recovery is  $<$ 66% of the subject’s baseline value (if known) [REDACTED], then the subject may remain on ITI at the discretion of the Investigator, up to a total duration of ITI of 33 months.

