**Figure 2: Immune Tolerance Induction Assessment Algorithm**

aSee Section 4.2.2.3 for complete Schedule of Activities for ITI.

bSee Section 10.2.5 for definitions of a positive low and high titer inhibitors.

cSee Section 10.2.7.4.1 for the definition of expected values, and Section 10.2.7.4.2 for ITI success criteria.

dSee Section 4.2.2.4 for Schedule of Activities for Half-Life Determination

eSee Section 4.2.2.5 for Schedule of Activities for Tapering Regimen.

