7.4.9. Response to Immune Tolerance Induction (ITI)

The ITI Analysis Set will be analyzed for response to the treatment regimen. Possible treatment responses are:

Complete Success

All of the following criteria are met:

1. Negative inhibitor titers in 2 consecutive determinations at least 28 days apart
2. IR $\geq 66\%$ of baseline in 2 consecutive determinations at least 28 days apart
3. $t_{1/2} \geq 6$ hours

Partial Success

The determination of partial success will be made only for patients who have completed 33 months of ITI but who do not fulfill the criteria for complete success. To achieve partial success, the following criteria must be met after patients have completed 33 months of ITI:

- Negative inhibitor titers on 2 consecutive determinations at least 28 days apart AND
- Either of the following (but not both):
 - IR $\geq 66\%$ of baseline in 2 consecutive determinations at least 28 days apart, or
 - $t_{1/2} \geq 6$ hours

Failure:

ITI failure is defined as the inability to meet criteria for Complete Success or Partial Success after 33 months on ITI.

Early Withdrawal/ITI Ongoing:

Patients may withdraw from the study during the ITI period before reaching 33 months or complete or partial success. In addition, any patients still in the ITI sub-study at the time of EoS or interim analysis will be included in this category.

Response categories of complete success, partial success, failure, and early withdrawal will be presented overall for the ITI Analysis Set, and separately for the inhibitor subgroups specified in Section 5.1.2.5, namely:

- Patients with high-titer inhibitors
- Patients with low-titer inhibitors that meet the clinically meaningful criteria
- Patients with high-titer inhibitors or low-titer inhibitors that meet the clinically meaningful criteria

Patients fulfilling the criteria for complete success will transition to a “tapering” regimen over a minimum period of 12 weeks with the aim of starting a prophylactic rFVIII Fc regimen, as described in [Section 10.2.7.5](#) of the protocol, and will be further monitored for relapse for up to 9 months as described in [Section 10.2.7.6](#) of the protocol.

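### The protocol puts 66% inside the definition of 'expected' recovery and then asks for 66% of expected, so it conflicts with its own partial-success text and with the SAP on the ITI recovery threshold

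*Protocol*

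**What the plan says.** The definition is in Protocol 10.2.7.4.1, which introduces it with "The reference IR Value (expected recovery), which is the basis for one of the criteria for complete ITI success, is defined below". The first bullet, for subjects with a value from the Baseline IR visit, gives at least 66% of that baseline value. The second bullet, after the word OR, is not visible in the public text.

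The definition is used in these places:

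- Protocol 10.2.7.4.2, complete success: IR must be at least "66% of expected in 2 consecutive determinations at least 1 month apart", together with negative titers and a half-life of at least 6 hours.
- Protocol 10.2.7.4.2, partial success: after 33 months, IR of at least 66% of expected is one of two alternatives. The other is the half-life.
- Protocol 4.2.2.3 and 4.2.2.4: confirmed IR of at least 66% of expected moves the subject to the next visit stage and starts the 12-weekly half-life assessments.
- Protocol Figure 2, footnote c: "See Section 10.2.7.4.1 for the definition of expected values".
- SAP 5.1.2.2, ITI visits: half-life evaluation also depends on IR of at least 66% of expected.

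Two places apply the percentage directly to baseline. The closing paragraph of the partial-success text begins "If the subject has 2 negative inhibitor tests but recovery is" and continues with below "66% of the subject’s baseline value (if known"; part of what follows is blacked out. Such a subject may stay on ITI at the Investigator's discretion. SAP 7.4.9 asks for IR of at least 66% "of baseline in 2 consecutive determinations at least 28 days apart", for complete success and for the IR route to partial success.

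**The concern.** A reference value is normally the quantity to which a percentage is applied. Here the reference already carries the percentage, and the criterion applies it again. Footnote c makes the link explicit, so a reader who follows the cross-reference arrives at a lower threshold than a reader of the SAP.

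The threshold drives decisions. It opens the next ITI visit stage, triggers half-life sampling, and is one of the three conditions for complete success, after which the child moves to tapering. It also classifies response to ITI, a named secondary endpoint. The ITI subset may be small, and one child placed in a different category could then visibly change the reported percentages. SAP section 10, which lists the major departures from the protocol, does not mention a change of reference from expected to baseline.

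**Working it through.** **Inputs.** B is the subject's baseline IR. The factor in the reference is at least 0.66 (Protocol 10.2.7.4.1). The factor in the criterion is 0.66 (Protocol 10.2.7.4.2, 4.2.2.3, 4.2.2.4). The SAP threshold is 0.66 x B (SAP 7.4.9). For illustration, B = 1.901 IU/dL per IU/kg, the geometric mean for children under 6 years (Protocol Table 1; 95% CI 1.785 to 2.024). The IR dose during ITI is 50 IU/kg (Protocol 10.2.7.1).

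**Step 1: reproduce the SAP figure.** Write expected = k x B, so that the protocol threshold is 0.66 x k x B. With k = 1 (expected is the baseline itself), the threshold is 0.66 x B. This matches SAP 7.4.9 and the closing partial-success paragraph.

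**Step 2: follow the cross-reference.** Section 10.2.7.4.1 gives k of at least 0.66. At the lower bound, 0.66 x 0.66 = 0.4356, or 43.6% of baseline. The gap to 66% is 66.0 - 43.56 = 22.4 percentage points.

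**Step 3: set the passages side by side.**

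| Passage | Threshold as a share of baseline |
|---|---|
| Protocol 10.2.7.4.2 criterion, read with 10.2.7.4.1 | 43.6% at the lower bound |
| Protocol 10.2.7.4.2, closing partial-success paragraph | 66% |
| SAP 7.4.9 | 66% |
| Protocol 4.2.2.3, 4.2.2.4 and SAP 5.1.2.2 | depends on what expected means |

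**Step 4: illustrate in IR units.**

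| B (IU/dL per IU/kg) | 0.66 x B | 0.4356 x B | Rise after 50 IU/kg (IU/dL) |
|---|---|---|---|
| 1.785 | 1.178 | 0.778 | 58.9 against 38.9 |
| 1.901 | 1.255 | 0.828 | 62.7 against 41.4 |
| 2.024 | 1.336 | 0.882 | 66.8 against 44.1 |

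**Step 5: consequence for one child.** Take IR confirmed at 50% of baseline with two negative titers, and suppose a half-life has been measured.

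- Half-life at least 6 hours: complete success on the twice-applied reading. On the once-applied reading it is not complete success; after 33 months it is partial success through the half-life route.
- Half-life under 6 hours after 33 months: partial success on the twice-applied reading, failure on the once-applied reading.

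Whether the schedule triggers a half-life measurement for this child at all depends on the same threshold.

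**The case against.** The strongest reply is that no document states 43.6%. The reference is written as an inequality, which cannot serve as a single denominator. The natural reading is that 10.2.7.4.1 spells out the recovery criterion and 10.2.7.4.2 restates it in short form. The closing partial-success paragraph supports this, because it treats a child below 66% of baseline as not yet recovered. Much of this stands. A reader might infer that the protocol sets a 43.6% threshold, or that a child in the band simply qualifies under the protocol. The documents do not support either inference: 43.6% arises only at the lower bound, and the protocol's own text contradicts it.

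A reader might also infer that sites and the analysis will in fact diverge. Protocol 10.2.7.1 has the Sponsor calculate IR and half-life and give them to the investigator, and Protocol 16.3 provides for real-time analysis to support the ITI outcome. That may limit divergence. It does not settle the matter, because no passage says which reference the value is judged against.

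Nor can Figure 2 itself be said to apply the percentage twice. Footnote c contains only a cross-reference, and the figure is not shown.

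Finally, IR alone does not start tapering, and the endpoint concerned is secondary and descriptive. That bears on weight. It does not remove a contradiction in a decision rule.

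**Conclusion.** The concern holds as an internal contradiction, not as evidence of a planned lower threshold. For subjects with a baseline IR, the definition and the criterion together give 43.6% of baseline at the lower bound, while the closing partial-success paragraph and SAP 7.4.9 give 66%. A single application is probably what was meant, but the section to which Figure 2 sends readers says otherwise. Children with IR between 43.6% and 66% of baseline, a band of 22.4 percentage points, could be classified differently depending on the passage followed.

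The conclusion rests on reading expected in 10.2.7.4.2 as defined in 10.2.7.4.1, as footnote c directs. The IR-unit figures are illustrative only, since they apply a group mean to a subject-specific reference. The documents do not allow an estimate of how many children would fall in the band. Nothing can be said about subjects without a baseline IR: SAP 5.1.4 refers to an absolute value, but it is not visible, and that is not a fault of the plan. The primary inhibitor endpoint and the sample size are unaffected. The correction should be made because the threshold is a decision rule.

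**What to change.** Reconcile Protocol 10.2.7.4.1, 10.2.7.4.2, 4.2.2.3, 4.2.2.4 and Figure 2 with SAP 5.1.2.2 and 7.4.9, so that the percentage is stated once, against one named reference. The clinical team should confirm the intended threshold, and the SAP should then use the same wording.

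The text not visible here must be checked in the same pass: the alternative for subjects without a baseline IR, the blacked-out part of the partial-success paragraph, and the redacted relapse criterion in Protocol 10.2.7.6. Editing the first bullet of 10.2.7.4.1 alone might leave its two bullets describing different kinds of quantity. It would also help to state in Protocol 10.2.7.1 which reference the Sponsor's calculated IR is judged against.

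The cost is a short protocol clarification, a matching SAP edit, and a letter to sites until the amendment is in force. No new data are needed.

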##### **10.2.7.4.2. Definitions of Complete Success, Partial Success, and Failure of Immune Tolerance Induction Therapy**

###### **Complete Success:**

CONFIDENTIAL

The information contained herein may not be used, disclosed, or published without the written consent of Bioerativ Therapeutics Inc.

Complete ITI success requires that all of the following criteria be met:

1. Negative inhibitor titers in 2 consecutive determinations at least 1 month apart
13. IR  $\geq$ 66% of expected in 2 consecutive determinations at least 1 month apart
14.  $t_{1/2} \geq$ 6 hours

Subjects may meet the criteria for complete success in less than 33 months.

Subjects fulfilling the criteria for complete success will transition to a “tapering” regimen over a minimum period of 12 weeks with the aim of starting a prophylactic rFVIII Fc regimen, as described in Section 10.2.7.5, and will be monitored for relapse for up to 9 months as described in Section 4.2.2.5.

**Partial Success:**

The determination of partial success will be made only for subjects who have completed 33 months of ITI but who do not fulfill the criteria for complete success.

To achieve partial success, the following criteria must be met after subjects have completed 33 months of ITI:

1. Negative inhibitor titers on 2 consecutive tests within 2 months of each other

AND

15. Either of the following but not both:

- IR  $\geq$ 66% of expected

OR

- $t_{1/2} \geq$ 6 hours

If the subject has 2 negative inhibitor tests but recovery is  $<$ 66% of the subject’s baseline value (if known) [REDACTED], then the subject may remain on ITI at the discretion of the Investigator, up to a total duration of ITI of 33 months.

**Failure:**

ITI failure is defined as the inability to meet criteria for Complete Success or Partial Success after 33 months on ITI.

**10.2.7.4.3. Algorithm for Determining the Outcome of Immune Tolerance Induction**

Assessments to be performed during the ITI regimen are described in Section 10.2.7.4. Additional assessments may be required, per Figure 2 below and the Schedule of Assessments in Section 4.2.2.3.

CONFIDENTIAL

[figure not shown]
The information contained herein may not be used, disclosed, or published without the written consent of Bioverativ Therapeutics Inc.

If subjects begin the ITI regimen but discontinue the regimen without meeting the criteria for successful immune tolerance, they will be withdrawn from the study. (See Section 11)

CONFIDENTIAL

The information contained herein may not be used, disclosed, or published without the written consent of Bioverativ  
Therapeutics Inc.

**Figure 2: Immune Tolerance Induction Assessment Algorithm**

aSee Section 4.2.2.3 for complete Schedule of Activities for ITI.

bSee Section 10.2.5 for definitions of a positive low and high titer inhibitors.

cSee Section 10.2.7.4.1 for the definition of expected values, and Section 10.2.7.4.2 for ITI success criteria.

dSee Section 4.2.2.4 for Schedule of Activities for Half-Life Determination

eSee Section 4.2.2.5 for Schedule of Activities for Tapering Regimen.

### 10.2.7.5. Transition to a Prophylactic Regimen Following Immune Tolerance Induction Therapy Success (Tapering Period)

Subjects fulfilling the criteria for complete ITI success will transition (“taper off”) to a prophylactic regimen over a minimum period of 3 months. The duration of the tapering period

CONFIDENTIAL

The information contained herein may not be used, disclosed, or published without the written consent of Bioerativ Therapeutics Inc.

may be modified by the Investigator with the Sponsor's medical monitor's approval based on the subject's clinical response.

The suggested "tapering" schedule is similar to that used on the International ITI Study protocol [Hay and DiMichele 2012]:

[REDACTED]

• [REDACTED]

• [REDACTED]

• [REDACTED]

*Prophylaxis Regimen during Follow-up:* Based on clinical response, adjust the prophylaxis regimen in the range of 25 to 65 IU/kg every 3 to 5 days, utilizing more frequent dosing or doses up to 80 IU/kg, as required.

#### 10.2.7.6. Monitoring for Relapse

During the 9-month period following the end of the tapering off (Section 10.2.7.5), the subjects will be monitored for relapse via blood samples processed by the central laboratory using the Nijmegen-modified Bethesda assay for inhibitor detection, as well as IR assessments. The inhibitor titer and IR will be measured every 3 months for the follow up period. rFVIII Fc half-life assessments will be performed 12 months after ITI success.

If any of these tests indicate the possibility of an inhibitor at any time between the start of tapering through the beginning of prophylaxis, the tests must be repeated within 2 to 4 weeks to confirm relapse.

Relapse is defined as any of the following, occurring within 12 months following complete ITI success, based on the International ITI criteria [Hay and DiMichele 2012]:

- A positive inhibitor ( $\geq 0.6$  BU/mL using the Nijmegen assay) that is confirmed by a second test result of  $\geq 0.60$  BU/mL from a separate sample, drawn approximately 2 to 4 weeks following the date when the original sample was drawn.
- [REDACTED]
- $t_{1/2} < 6$  hours.

#### 10.2.8. Surgery

For subjects who require emergent or elective surgery during the study period, the target FVIII levels for the proposed procedure will be those deemed appropriate by the Investigator for the

CONFIDENTIAL

The information contained herein may not be used, disclosed, or published without the written consent of Bioverativ Therapeutics Inc.

type of surgery to be performed. Recommendations for the appropriate dosing regimen of rFVIII Fc during the surgery may be discussed between the Investigator and the Medical Monitor taking factors such as standard doses of FVIII for the type of surgery, the clinical status of the subject, and IR data for the subject into consideration.

All doses administered in the hospital will be captured in the eCRF. The subject's parent/caregiver should not enter these doses in the EPD.

See Section 4.2.2.6 for the surgery visit schedule.

#### **10.2.8.1. Definitions of Major and Minor Surgery**

Surgeries, elective or emergent, will be classified as major and minor as follows:

- Major surgery is defined as any surgical procedure in which a major body cavity is penetrated and exposed or for which a substantial impairment of physical or physiological function is produced (e.g., laparotomy, thoracotomy, craniotomy, joint replacement, or limb amputation).
- Minor surgery is defined as any surgical procedure that does not qualify as major (e.g., minor dental extractions, incision and drainage of abscess, port placement, or simple excisions).

#### **10.2.8.2. Definition of the Surgical Period**

The surgical period includes Preoperative, Intraoperative, and Postoperative Periods:

- The preoperative period of the study (that is, the beginning of the surgical period) begins with the first dose of rFVIII Fc given for the surgery. For elective surgeries, this is the pre-surgery dose.
- The intraoperative period is defined as the time from when the surgery begins to the time when the surgery is completed.
- The postoperative period is defined as the time period following the end of surgery through the last dose of rFVIII Fc given for the surgery, as judged by the Investigator/Surgeon, including doses given to prevent bleeding during the postoperative period.

##### **10.2.8.2.1. Minor Surgery**

Minor surgery is allowed at any time during the study.

For minor surgeries, pre-surgery assessments of FVIII trough and recovery, inhibitor, and anti-rFVIII Fc antibody, and hematology and blood chemistry on the day of surgery are only to be performed if indicated by the nature of the procedure, according to local standard of care.

CONFIDENTIAL

The information contained herein may not be used, disclosed, or published without the written consent of Bioerativ Therapeutics Inc.

If FVIII activity levels and inhibitor formation assessments are indicated, predose samples will be collected prior to the dose of rFVIII Fc given for the surgery, and FVIII recovery levels will be sampled 30 ( $\pm$ 5) minutes after the start of the rFVIII Fc injection.

Bleeding caused directly by surgery should not be reported, although undesired or unexpected bleeding during or after surgery should be recorded on the eCRF. The Investigator or Surgeon's assessment of response will be conducted on the day of surgery.

The Investigator will contact the subject's parent/caregiver after the day of surgery to determine when the subject returns to his regular dosage regimen.

#### **10.2.8.2.2. Major Surgery**

Major surgery will only be allowed in the study after the subject has had at least 3 injections of rFVIII Fc without safety concerns. If a subject needs to undergo major surgery prior to 3 injections, they will be withdrawn from the study. The Investigator must consult with Bioverativ in advance of the surgery.

All major surgeries must take place in a center that can provide study treatment, trained study personnel, postoperative assessments, and hematological consult by the Investigator or Sub-Investigator. If surgery does not take place in such a setting, the subject will be withdrawn from the study.

In addition, subjects who require major surgery may receive rFVIII Fc if:

1. The surgery occurs within the contracted institution for the study and/or a separate agreement has been executed, permitting the use of study drug and Bioverativ's rights to data generated in the study at an alternative institution deemed appropriate by the Principal Investigator or designee.
2. The Investigator and/or appropriate qualified/licensed delegate is available to:
  - a. Administer all rFVIII Fc doses required during surgery and during postoperative rehabilitation (if applicable).
  - b. Provide medical oversight and guidance throughout the duration of the preoperative and the intraoperative periods.

All major surgeries will be reported as SAEs, even if the surgery does not otherwise meet the definition of an SAE.

Samples for determination of predose FVIII activity levels and inhibitor formation will be collected prior to the dose of rFVIII Fc given for the surgery, and FVIII recovery levels will be sampled 30 ( $\pm$ 5) minutes after the start of the rFVIII Fc injection.

For major surgeries, a repeat blood draw for FVIII activity should be taken approximately 9 hours after the start of the injection, but may alternatively follow local standard of care for determining when the next dose of rFVIII Fc should be administered. While hospitalized, blood

CONFIDENTIAL

The information contained herein may not be used, disclosed, or published without the written consent of Bioverativ Therapeutics Inc.

will be drawn daily to be tested at the local laboratory for FVIII activity so that monitoring of the subject can occur in real time.

Bleeding caused directly by surgery should not be reported, although undesired or unexpected bleeding during or after surgery should be recorded on the eCRF. The Investigator or Surgeon's assessment of response is conducted 24 hours after surgery and at the Postoperative Visit (1 to 2 weeks after surgery).

A postoperative visit will be required following major surgery.

